6.5.3 Treatment Guidelines for QTc Prolongation

Immediate medical management of patients will be based on the following:

- a. Baseline: A pre-infusion (baseline) ECG will be obtained on all patients, if the automated measurements indicate a QTcF of ≥ 450 msec
- b. The single QTcF will be verified by manually measuring at least 3 complexes within the ECG and determining the average QTcF
- c. All patients must have a pre-infusion QTcF of < 450 msec by either: Calculation using the automated measurements of the first ECG or the manual measurement of a single ECG
- d. If it is determined that the manually read QTcF ≥ 450 msec, the Principal Investigator should be contacted to discuss the clinical significance of the reading and to determine if it is appropriate to move forward with the infusion.
- e. During treatment: Grade 3 QTc prolongation (any QTcF that is ≥ 501 msec OR > 60 msec QTcF increase relative to pre-infusion) will be manually verified by measuring at least 3 complexes with the ECG and determining the average QTcF. If QTcF prolongation is \geq Grade 3, an ECG may need to be repeated more frequently

during a patient's visit, depending on the degree of the prolongation, as indicated in this section and per institutional standards.

Note: Dose modification will be based on the average QTcF using the manual measurements.

- f. If the Investigator has any question regarding the local automated reading, a local cardiologist should be consulted. Treatment guidelines for patients experiencing QTc prolongations are provided in this section below.
- g. Patients who experience \geq Grade 3 QTc prolongation must be assessed by the Investigator (or qualified designee) prior to discharge.

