6.5.4 Treatment Guidelines for QTc Prolongation

QTc Prolongation	After Tarloxitinib Administration
Grade 1 450 to 480 msec QTcF	
 • Cycle 1 and Cycle 2 Day 1 
 ◦ May be discharged if the 4-hour (or later) post-infusion QTcF is Grade 1 or lower and asymptomatic • After Cycle 2 Day 1 
 ◦ Obtain pre-infusion and 2-hour post-infusion ECGs ◦ May be discharged if the 2-hour (or later) post-infusion QTcF is \leq Grade 1 and the patient is asymptomatic • Continue the same tarloxitinib dose for subsequent cycles
Grade 2 481 to 500 msec QTcF	
 • Cycle 1 and Cycle 2 Day 1 
 ◦ May be discharged if the 4-hour (or later) post-infusion QTcF is \leq Grade 2 and the patient is asymptomatic • After Cycle 2 Day 1 
 ◦ Obtain pre-infusion and 2-hour post-infusions ECGs ◦ May be discharged if the 2-hour or later post-infusion QTcF is \leq Grade 2 and the patient is asymptomatic • Continue the same tarloxitinib dose for subsequent cycles

Grade 3 ≥ 501 msec QTcF	
 Obtain ECGs every 15 to 30 minutes until QTcF is \leq Grade 2 and then obtain ECGs every 1 hour May be discharged home if 2 subsequent measurements (at least 15 minutes apart) after the 4-hour post-infusion QTcF is \leq Grade 2 and no significant arrhythmias 
 If QTcF is ≥ 601 msec, permanently discontinue tarloxitinib If QTcF ≥ 501 msec and ≤ 600 msec 
 Resume tarloxitinib dosing with dose reduction 
 1st occurrence: reduce to 100 mg/m² 2nd occurrence: reduce to 75 mg/m² 3rd occurrence: permanently discontinue tarloxitinib Obtain ECGs prior to and hourly (for at least 4 hours) following the next tarloxitinib infusion
Grade 3 > 60 msec increase from pre-infusion QTcF AND ≤ 500 msec QTcF	
 Obtain ECGs every 15-30 minutes until QTcF is \leq Grade 2 and then obtain ECGs every 1 hour May be discharged home if 2 subsequent measurements (at least 15 minutes apart) after the 4-hour post-infusion QTcF is \leq Grade 2 and no significant arrhythmias 
 Obtain ECGs prior to and hourly (for at least 4 hours) following the next tarloxitinib infusion

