Grade 4 TdP or polymorphic ventricular tachycardia, signs/symptoms of serious arrhythmia	
 Place patient on telemetry and obtain ECGs as clinical indicated Obtain Cardiologist consult and admit to hospital for extended observation on telemetry Permanently discontinue tarloxitinib

ECG = electrocardiogram; msec = millisecond; QTcF = corrected QT interval as calculated according to Fridericia's formula; TdP = Torsade de Pointes

Note: If QTcF prolongation is \geq Grade 3, an ECG may need to be repeated more frequently during the patient's visit depending on the degree of the prolongation and per institutional standards.

Treatment and retreatment guidelines in this study are based on absolute QTcF observations that vary from the NCI CTCAE. Importantly, dose reductions are not based on the QTcF change from baseline, only the absolute QTcF. For example, if a patient has a change > 60 msec from baseline but has an absolute QTcF ≤ 500 msec, no dose reduction is required.

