*** Every 8 weeks (+/- 5 days) from Cycle 1 Day 1***

Every visit

Every visit

CT = Computed tomography, ECOG = Eastern Cooperative Oncology Group, EOI = End of Infusion, EOT = End of Treatment, SFU = Safety Follow-up, MRI = Magnetic Resonance Imaging, PET= Positron Emissions Tomography, QTcF = Corrected QT interval as calculated according to Fridericia's formula, SCR = Screening period

¹ For patients with Grade 3 QTcF prolongation (≥ 501 msec or > 60 msec increase compared to pre-infusion), repeat ECG every 15 to 30 mins until resolved to Grade 2 (481 to 500 msec) or lower (≤ 480 msec) and then obtain ECGs every hour up to 4 hours post infusion, or longer as clinically indicated.

² Serum pregnancy test at baseline, then urine pregnancy test, for women of childbearing potential

³ Collect blood for biomarkers per correlates manual.

⁴ If required. See section 7, potassium supplementation.

⁵ Perform radiographic assessments according to institutional practice. Include CT or MRI of the chest and abdomen, and if applicable, brain CT or MRI, bone scan, or PET-CT at screening. The baseline tumor assessment is required within 28 days prior to first dose of tarloxotinib. PET-CT may be substituted for a contrasted CT of the chest and abdomen if tumor measurements are obtained per RECIST 1.1 criteria. The same imaging modality used for baseline imaging must be used for subsequent tumor assessments in each patient.

⁶The EOT visit should be conducted within +/- 7 days of the last dose of tarloxotinib, and the safety follow-up should occur 30 days (+/- 7 days after the last dose of tarloxotinib).

⁷Patients may be followed for survival status every 3 months for up to 6 months after the last patient on study visit (LPV) at the investigator's discretion.

⁸Informed consent, medical history and physical exam/ECOG status to be obtained within 28 days of Cycle 1 Day 1. Baseline labs and ECG are to be obtained within 14 days of Cycle 1 Day 1.

⁹ Vital signs should include: Height (at screening only), weight, blood pressure, temperature, respirations, and O₂ saturation.

¹⁰ Liver function testing to be performed every 3 weeks for the first 3 months, then monthly as clinically indicated.

Cycles are 28 days in length. Study visits have a +/- 1 day window to allow for holidays or other rescheduling reasons, to be documented in the research record.

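### In the rise-only Grade 3 row of 6.5.4, the printed stop for the 15-30 minute ECGs is already met on entry, so that step does not operate as printed

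*Combined protocol and SAP*

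**What the plan says.** The 6.5.4 table splits Grade 3 QTc prolongation into two rows. The first is for QTcF of 501 msec or more. The second is entered on more than a "60 msec increase from pre-infusion QTcF AND" an absolute QTcF of at most 500 msec. Both rows order ECGs at 15 to 30 minute intervals until Grade 2 or lower, then hourly; in the second row the instruction begins "Obtain ECGs every 15-30 minutes until QTcF is".

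The table's Grade 2 band is "481 to 500 msec QTcF" and its Grade 1 band is 450 to 480 msec. Neither band limits the change from pre-infusion.

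Footnote 1 of the study calendar in 9.2 names both Grade 3 triggers and gives one numerical stop for them: "repeat ECG every 15 to 30 mins until resolved to Grade 2 (481 to 500 msec) or lower", the last part glossed as at most 480 msec. It continues: "and then obtain ECGs every hour up to 4 hours post infusion, or longer as clinically indicated".

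Two other places bear on the reading. Section 6.5.3(e) counts a more than "60 msec QTcF increase relative to pre-infusion" as Grade 3 in its own right. The note below the 6.5.4 table says: "Treatment and retreatment guidelines in this study are based on absolute QTcF observations that vary from the NCI CTCAE". That note then gives an explicit rule and an example, both about dose reduction.

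**The concern.** A stop rule should describe a state that the patient is not yet in. Here the condition that admits a patient to the row includes the condition that ends the frequent ECGs. A site that follows the printed values would find the step finished before the first repeat ECG.

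What is at stake is close observation after a large acute rise. QTc prolongation is the most frequent tarloxotinib event in the toxicity table of 3.1.7: 60.9% at any grade and 34.8% in the column headed >G3 (n=23, monotherapy). As far as the calendar table can be read, ECGs at 1, 2, 3 and 4 hours after the end of infusion are scheduled anyway. If so, the 15-30 minute step is the main ECG monitoring that this row adds in the first four hours.

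**Working it through.** The plan gives no figure to reproduce. This is a check of logic.

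**Inputs.** Let p be the pre-infusion QTcF and q the post-infusion QTcF, in msec.
- Entry to the row (6.5.4): q − p > 60 and q ≤ 500.
- Printed stop (6.5.4 bands; footnote 1 in 9.2): q ≤ 500, that is, 481 to 500 or lower.
- Pre-infusion limit (6.5.3(c)): p < 450.

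**Step 1: the implication.** Entry requires q ≤ 500, and the stop is q ≤ 500. Entry therefore implies the stop for every p, and no modelling assumption is needed. In the other Grade 3 row, entry is q ≥ 501, which fails q ≤ 500, so the same wording works there.

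**Step 2: an example.** With p = 420 and q = 485, the rise is 485 − 420 = 65 msec. That is Grade 3 by this row, yet 485 lies inside the printed Grade 2 band.

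**Step 3: enumeration, as illustration only.** Take whole-msec values of p from 350 to 449. The lower end of 350 is an assumption; no document gives it. For each p the row admits q = p + 61 to 500, which is 440 − p values. The sum for p = 350 to 439 is 90 + 89 + ... + 1 = 90 × 91 / 2 = 4095 states.

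| Where q lies | States |
|---|---|
| below 450 | 780 |
| 450 to 480 | 1705 |
| 481 to 500 | 1610 |
| Total | 4095 |

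- Printed stop, q ≤ 500: met on entry in 4095 of 4095.
- Stop that also needs q − p ≤ 60: met on entry in 0 of 4095.

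These are logical states, not patient frequencies. A different lower bound changes 4095 but neither proportion.

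**Step 4: the upper edge.** At p = 439 the first qualifying value is 439 + 61 = 500. At p = 440 it is 501, which belongs to the other row. The rise-only row is thus empty from p = 440 upward, and exceptions at p ≥ 450 under 6.5.3(d) do not alter the result.

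**Step 5: how large a rise fits under the printed stop.** The largest is 500 − p: 120 msec at p = 380, 100 at p = 400, 80 at p = 420. With a 60 msec limit on the rise, the step would end at p + 60: 440, 460 and 480.

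**The case against.** **The row can be read so that it works.** It is headed Grade 3, and 6.5.3(e) and footnote 1 both count the rise alone as Grade 3. A patient whose rise still exceeds 60 msec is then not yet at Grade 2 or lower, and the frequent ECGs continue. Footnote 1 also speaks of resolving, which presupposes a change from the entry state. This reading is possible and is probably what a careful clinician would do. But no place states a rise of 60 msec or less as the stop, and footnote 1 prints absolute numbers for both triggers. Two sites could each follow the text and act differently.

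**The absolute basis is declared.** The opening sentence of the note below the table covers treatment guidelines generally, not only dosing. This stands as far as it goes, but if it governs monitoring too, the row orders a step that can never run. The text would need correcting on that view as well.

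**Discharge.** The row says: "May be discharged home if 2 subsequent measurements (at least 15 minutes apart) after the 4-hour post-infusion QTcF is" at Grade 2 or lower, with no significant arrhythmias. A reader might infer that this rule is equally defective, since someone whose rise has not fallen can pass its QTcF part. The documents do not support calling that an error. Discharge on an absolute value agrees with the note, and requiring the rise to fall is a clinical choice. The row also remains stricter than the Grade 2 row, under which, after Cycle 2 Day 1, a single 2-hour reading can suffice. Investigator assessment before discharge (6.5.3(g)) applies throughout.

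**Conclusion.** The point holds for the 15-30 minute ECG step. As printed, its stop is satisfied on entry by every patient in the rise-only row, so the step has no effect. This rests on footnote 1's numbers being applied as written.

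The consequence is confined to early ECG frequency. Hourly ECGs to 4 hours or longer, the two readings after the 4-hour ECG, and hourly ECGs at the next infusion all remain. More frequent ECGs at Grade 3 or above are also foreseen, though at discretion. A reader might infer that these patients go unmonitored; they do not.

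Nor should 34.8% be read as the share affected. That figure is from monotherapy and is not split between absolute and rise-only events, so the number of patients concerned is unknown. Dosing is settled by the note below the table: with QTcF at or below 500 msec, a rise above 60 msec calls for no dose reduction. That is deliberate and not part of this point. No effect on any endpoint or analysis follows.

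**What to change.** 1. In the rise-only Grade 3 row of 6.5.4, and in footnote 1 of the 9.2 calendar for patients who enter on the rise, end the 15-30 minute ECGs when QTcF is at most 500 msec **and** the rise from pre-infusion is at most 60 msec.
2. In the note below the 6.5.4 table, state that the absolute-QTcF basis governs dose reduction and retreatment, not this monitoring stop. Without this, the new stop would conflict with the note.
3. Have the clinical team decide, and write down, whether discharge should also need a rise of at most 60 msec. Because footnote 1 covers both triggers, they should also say whether the rise condition applies to patients who entered at 501 msec or more.

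Leave the hourly, next-infusion and dosing rules as they are.

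**Cost.** Wording in one row, one footnote and one note. ECGs every 30 or 15 minutes are 2 or 4 per hour against 1 per hour, so 1 to 3 extra per hour while the rise persists. Over a full 4 hours that is 8 to 16 against 4, or 4 to 12 extra. If the team also ties discharge to the rise, some patients would stay longer.

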6.5.5 Treatment Guidelines for Infusion-related Reactions

Treatment and management of infusion-related reactions will be based on the severity and type of symptom(s) experienced. Treatment guidelines for infusion-related reactions are presented in the table below.

Grade (CTCAE v5.0)	Definition	Treatment Guideline
Grade 1	
 • Mild transient reaction • Infusion interruption not indicated • Intervention not indicated 	
 • Monitor for at least 2 hours after the end of the infusion • Provide patient instructions and prophylactic medications at discharge as appropriate • Consider adjusting premedication based on symptoms for subsequent infusions
Grade 2	
 • Therapy or infusion interruption indicated but responds promptly to symptomatic treatment • Prophylactic medications indicated for ≤ 24 hours 	
 • Interrupt tarloxitinib infusion • Administration of medications (e.g., anti-histamines, steroids, NSAIDs and IV fluids), as appropriate • Monitor for at least 2 hours after the end of the infusion • Consider adjusting premedication based on symptoms for subsequent infusions • After symptoms resolve to baseline, resume future tarloxitinib infusions to 50% of the initial infusion rate

Grade 3	
 • Prolonged (e.g., not rapidly responsive to symptomatic medication and/or brief interruption of infusion) • Recurrence of symptoms following initial improvement, hospitalization indicated for clinical sequelae 	
 • Interrupt tarloxitinib infusion • Administration of medications (e.g., anti-histamines, steroids, NSAIDs and IV fluids), as appropriate • Hospitalization for medical care and observation • Reduce tarloxitinib dose to 120 mg/m² for subsequent doses*, and/or adjusted premedication after discussion with the Principal Investigator • If Grade 3 infusion reaction recurs after this initial dose reduction, then reduce the tarloxitinib dose to 75 mg/m² for subsequent doses • After symptoms resolve to baseline, resume future tarloxitinib infusions to 50% of the initial infusion rate
Grade 4	
 • Life-threatening consequences • Urgent intervention indicated 	
 • Hospitalization for urgent medical treatment • Discontinue tarloxitinib permanently

CTCAE = Common Terminology Criteria for Adverse Events; IV = intravenous; NSAID = nonsteroidal anti-inflammatory drug

* Dose re-escalation may be permitted following discussion and approval by the Principal Investigator

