6.5 TREATMENT AND RETREATMENT CRITERIA

The results of tumor assessments are not required for the initiation of subsequent cycles, but patients must meet the following criteria before receiving each tarloxotinib infusion. **Note:** all ECG dose modifications will be based on the average manually measured QTcF.

- No QTcF of \geq 601 msec during any previous infusion

Note: Patients with QTcF of \geq 501 msec and $<$ 601 msec during or following the prior infusion MUST be dose reduced. If QTcF prolongation is \geq Grade 3, an ECG may need to be repeated more frequently during a patient's visit as clinically indicated, depending on the degree of the prolongation and per institutional standards.

- Check serum electrolytes
 - Pre-infusion magnesium and calcium in normal range, unless an exception is approved by the Principal Investigator.
 - If other electrolytes (e.g., sodium, chloride) are outside of the normal range, patient can receive tarloxotinib infusion if it is deemed safe per Investigator discretion.
 - Pre-infusion serum potassium must be \geq 3.5 mEq/L.
- Pre-infusion ECG: No evidence of second- or third-degree atrioventricular block
 - QTcF interval of $<$ 450 msec
- Skin rash of \leq Grade 2
- Gastrointestinal toxicity of \leq Grade 2
- Any other clinically significant tarloxotinib-related toxicity must return to at least Grade 2.

All patients not meeting retreatment criteria must be discussed with the Principal Investigator and possible dose/schedule modification and/or study treatment discontinuation discussed.

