6.5.2 Tarloxotinib Dose Modifications

All patients will receive a weekly tarloxotinib infusion at the RP2Dc determined in the safety lead-in portion of the trial administered as a weekly 1-hour IV infusion on Days 1, 8, 15, and

22 of each 28-day cycle until disease progression or unacceptable toxicity. All patients will begin study treatment based on the body weight measured on Day 1 of each cycle (or within 7 days prior [e.g., Day 22 of the prior cycle]). As described above, tarloxotinib dose calculations do not need to be adjusted within a cycle unless the patient has a > 10% change in body weight. Other dose modifications may be required based on QTc prolongation, infusion-related reactions, and other tarloxotinib-related toxicity as described below.

Dose level reductions will be in a step-wise fashion. If a patient requires more than 2 dose level reductions, tarloxotinib will be permanently discontinued.

Hematologic toxicity has not been associated with tarloxotinib administration to date. However, if Grade 3 or 4 neutropenia or thrombocytopenia considered related to tarloxotinib occurs, then the treatment guidelines for non-hematologic toxicity should be followed. Dose modifications for anemia (any grade) or for Grade 2 or less neutropenia or thrombocytopenia are not required.

If a tarloxotinib-related toxicity results in a treatment delay of more than 3 weeks (withholding more than 2 doses of tarloxotinib), patients will be removed from study treatment unless otherwise approved by the Principal Investigator.

Should a dose reduction for sotorasib be required, given the potential for overlapping toxicities and challenges in attributing toxicities to one drug in a combination therapy, a dose reduction in tarloxotinib should also be considered.

Dose level	Sotorasib	Tarloxitinib
0 (full dose)	960 mg PO daily	150 mg/m ² IV weekly
-1	480 mg PO daily	100 mg/m ² IV weekly
-2	240 mg PO daily	75 mg/m ² IV weekly

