6.5.6 Treatment Guidelines for Other Non-Hematologic Toxicity

The table below provides treatment guidelines for treating tarloxitinib non-hematologic toxicities other than QT prolongation and infusion-related reactions.

Toxicity (CTCAE v5.0)	Details	Hold Dose	Dose Levels After Recovery to \leq Grade 2 or Baseline
Grade 2	Intolerable skin toxicity or diarrhea	Hold dose until resolution to Grade 0 or 1 or Grade 2 tolerable	If symptoms are intolerable, recurrent, or not controlled by supportive care, hold dose until symptoms improve and reduce to next lower dose level
Grade 2	ALT or AST $> 3 \times$ ULN	Hold dose until resolution to $<$ Grade 2 or baseline	150 mg/m ² (no reduction)
	ALT or AST $> 3 \times$ ULN (Grade 2) AND a total bilirubin $\geq 2 \times$ ULN (patients without liver metastasis)**	Treatment to be discontinued	Not applicable
Grade 3	Nausea and vomiting*	Hold dose until resolution to Grade 0 or 1 or Grade 2 tolerable	120 mg/m ² ; if recurs, then second reduction to 75 mg/m ²
Grade 4	Pulmonary embolism that is adequately treated	Hold dose until resolution to Grade 0 or 1	120 mg/m ² ; if recurs, then second reduction to 75 mg/m ²
Grade 4	All other life-threatening conditions	Treatment to be discontinued	Not applicable

ALT = alanine aminotransferase; ASP = aspartate aminotransferase; CTCAE = Common Terminology Criteria for Adverse Events; ULN = upper limit of normal

* May hold or reduce if nausea/vomiting continues despite optimized anti-emetic treatment

** Tarloxitinib-related toxicity meeting the definition of Hy's Law, tarloxitinib will be discontinued permanently

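### The fixed tarloxotinib doses in 6.5.4 to 6.5.6 fit only a patient currently at 150 mg/m², and for patients at 100 or 75 they conflict with the protocol's own reduction rules

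*Combined protocol and SAP*

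**What the plan says.** The dose-level tables in the schema, 6.1 and 6.5.2 list tarloxotinib at 150, 100 and 75 mg/m² and nothing else. Section 6.5.2 sets the treatment dose: "All patients will receive a weekly tarloxotinib infusion at the RP2Dc determined in the safety lead-in portion of the trial". Under 11.1 that dose can be below 150. Two or more DLTs at 150 send the next lead-in patients to DL -1 (100), and the RP2D_c is the highest level with at most 1 DLT in 6. Section 11.1.1 lets the RP2D_c be revised during expansion.

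The tables that follow give fixed doses, none of them conditioned on the patient's current dose:

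- **QTcF 501 to 600 msec (6.5.4):** "1st occurrence: reduce to 100 mg"/m², then 75, then stop.
- **Grade 3 infusion reaction (6.5.5):** "Reduce tarloxitinib dose to 120 mg"/m², then 75 on recurrence.
- **Grade 3 nausea/vomiting and treated Grade 4 pulmonary embolism (6.5.6):** 120, and "if recurs, then second reduction to 75 mg"/m².
- **Grade 2 ALT/AST (6.5.6):** after recovery, 150, labelled as no reduction.

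Two general rules sit alongside. Section 6.5 says that a patient with QTcF of at least 501 and below 601 msec "during or following the prior infusion MUST be dose reduced". Section 6.5.2 makes reductions step-wise by level and stops tarloxotinib when a patient needs more than two. One row in 6.5.6, for intolerable Grade 2 skin toxicity or diarrhea, is already relative: "hold dose until symptoms improve and reduce to next lower dose level".

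**The concern.** The fixed entries are correct only if the patient is at 150 when the toxicity occurs. The lead-in exists to find out whether 150 is tolerable, so a start at 100 is an outcome the protocol plans for. A patient can also be at 100 when the RP2D_c is 150, after an earlier reduction for another toxicity.

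For those patients the tables name a dose that is not a reduction. The QTc row matters most, because it covers serious prolongation of 501 msec or more, reduction there is mandatory, and the row itself calls for no discussion with the Principal Investigator. A site dosing from the table would find an entry that contradicts both 6.5 and the row's own heading line, which says that dosing resumes at a reduced dose.

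**Working it through.** The plan states no computed figure on this point. The check compares each fixed target with each possible current dose.

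**Inputs.** Defined levels 150, 100 and 75 (schema, 6.1, 6.5.2). Fixed targets: 100 for the first QTc step (6.5.4), 120 (6.5.5, 6.5.6) and 150 for ALT/AST (6.5.6).

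**Formula.** Change = target / current dose − 1.

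| Current dose (mg/m²) | QTc 1st step, to 100 | 120 target | ALT/AST entry, 150 |
|---|---|---|---|
| 150 | 100/150 − 1 = −33.3% | 120/150 − 1 = −20% | 0% |
| 100 | 100/100 − 1 = 0% | 120/100 − 1 = +20% | 150/100 − 1 = +50% |
| 75 | 100/75 − 1 = +33.3% | 120/75 − 1 = +60% | 150/75 − 1 = +100% |

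Every entry works from 150. From 100 or 75, none of the QTc first-step or 120 entries lowers the dose, and the ALT/AST entry does not hold it constant. The step-wise rule would instead take a patient from 100 to 75, which is 75/100 − 1 = −25%.

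**When this arises with RP2D_c = 150.** A patient cut from 150 to 100 for QTc who then has a Grade 3 infusion reaction is pointed to 120. A patient cut to 100 for intolerable Grade 2 rash who then has a first QTc event is pointed to 100. The documents give no figure for how often either would happen.

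**How likely is a start at 100?** Under 11.1, 150 is abandoned if 2 or more of 6 patients have a DLT. Two among the first three already decide it, so the probability is the same:

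P(150 abandoned) = 1 − [(1 − p)⁶ + 6p(1 − p)⁵]

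The documents give no DLT rate for the combination, so p is an assumption:

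- p = 10%: 1 − (0.531 + 0.354) = 0.114, or 11%
- p = 20%: 1 − (0.262 + 0.393) = 0.345, or 34%
- p = 30%: 1 − (0.118 + 0.303) = 0.580, or 58%

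If 150 is abandoned, at least 3 lead-in patients start at 100. If the RP2D_c is then 100, the whole expansion cohort of up to 12, eligible lead-in patients at that level included, starts there.

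**The case against.** The strongest reply is that the protocol already supplies the right dose. Section 6.5.2 does defer to later text: "Other dose modifications may be required based on QTc prolongation, infusion-related reactions, and other tarloxotinib-related toxicity as described below". But what follows directly is the step-wise rule, the limit of two reductions and the table of levels. For a patient at 100, the only defined lower level is 75. It is also the only dose that satisfies 6.5, 6.5.2 and the heading line of the QTc row together. This largely stands. A reader might infer that the protocol directs re-treatment at an unreduced dose, or even an increase. The documents do not support that: re-treating at 100 would break two explicit instructions, and 6.5.5 says to reduce.

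The 120 entries are also softer than they look. In 6.5.5 the cut is an and/or alternative to adjusted premedication, after discussion with the Principal Investigator. The nausea/vomiting footnote in 6.5.6 makes holding or reducing discretionary. Only the pulmonary embolism entry offers no such latitude.

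Nor is the counting of 120 as open as its absence from the level table suggests. Section 6.5.5 treats it as the initial reduction, 6.5.6 calls 75 the second, and the limit in 6.5.2 is per patient. What remains unstated is how a re-escalation counts: "Dose re-escalation may be permitted following discussion and approval by the Principal Investigator".

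What the objection does not remove is the mismatch itself. No text says that the step-wise rule overrides the tables, and 120 shows that the tables do depart from the defined levels.

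**Conclusion.** The point holds as an internal conflict. The fixed entries in 6.5.4 to 6.5.6 are right from 150 and wrong from 100 or 75. For a patient at 100 the first QTc step changes nothing, the 120 target is 20% too high to be even a null step, and the ALT/AST entry is 50% above the current dose. When the RP2D_c is 150, the QTc row is correct for any patient not already reduced.

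The 11%, 34% and 58% figures might be read as a chance of misdosing. They are only the chance that 150 is abandoned at assumed DLT rates of 10%, 20% and 30%. They say nothing about how many patients at 100 would meet one of these toxicities, or whether a site would follow the table over the general rule. A site can probably resolve the conflict, and an actual increase is unlikely.

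This should be fixed, because it concerns a safety dosing rule in a scenario the protocol plans for. It does not rise to a fault that must be cured before the trial can proceed. Sample size, error rates and analyses are not affected.

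**What to change.** - **6.5.4:** replace the fixed QTc doses with a move to the next defined level down, using the relative wording already in the skin/diarrhea row of 6.5.6. Discontinue at the third occurrence or when no lower level remains, whichever comes first. Nothing changes for a patient at 150 who has not already been reduced.
- **6.5.5 and 6.5.6:** keep 120 only for patients currently at 150. For patients at 100 or below, use the next defined level down.
- **6.5.6, Grade 2 ALT/AST:** say that treatment resumes at the patient's current dose.

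Two further changes are optional. One is to replace 120 by 100 for patients at 150, which deepens that cut from 20% to 33%. The other is to state in 6.5.2 how reductions and re-escalations are counted across toxicities.

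The cost is edits to three tables in one amendment, plus site notification. There is one clinical consequence. QTc discontinuation now falls at the third occurrence. It would move to the second for a patient starting at 100 (75, then stop), and to the first for one starting at 75, unless a lower level is defined. Section 11.1 already allows levels below DL -2 to be considered. The sponsor needs to agree to this on clinical grounds.
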